5.3.3 Exploratory Analyses

It is possible that the beneficial effects of the study drug, if observed, will be more evident in one subset of patients than another. To assess this possibility, we will conduct a series of analyses, categorizing patients into a variety of clinical sub-groups: first episode vs. recurrent episode of ureterolithiasis; small stones (<1.9mm) vs. moderate stones (2-5.9mm) vs. large stones (>6mm); location of stone; male patients vs. female patients; age. These will be tested as interactions with treatment group, using cross-product terms, in a Cox proportional hazards model to assess the duration of symptoms.

5.3.4 Statistical Complications

Because of the brief treatment and follow-up period and the expected very low rate of side effects, it is anticipated that the attrition rate will be low. However, if any patients end their treatment early while still providing outcome information, the primary outcome will be analyzed according to the intention-to-treat principle. It is possible that some outcome data may be missing for some patients. For example, some patients may not be reachable by telephone, may refuse to provide follow-up information or may have unreliable recall. If the number missing is low these patients will be dropped from the analysis; otherwise multiple imputation methodology⁵⁹ will be employed to reduce statistical bias and make efficient use of all of the data.

5.4 Sample Size and Power

5.4.1 Sample size

The primary outcome for the STONE study is the proportion of patients who pass stones within 28 days. Data on stone passage rates is summarized in a meta-analysis by Hollingsworth et al³⁷ who found the baseline occurrence of stone passage in the control group across nine studies to be 47% with rates ranging from 20% to 73%. The lower confidence limit of the passage rate in the treatment group across the nine studies was 68%. A two group chi-squared test with a 0.05 two-sided significance level will have 90% power to detect the difference between a placebo proportion of 0.45 and a tamsulosin proportion of 0.60 when the sample size in each group is 250 accounting for losses to follow-up.

Due to concerns that the passage rate might be inappropriate, this sample size will be achieved in a two-stage approach. After the outcomes of the treatment of the first 100 patients were obtained, the passage rate in the placebo group was calculated by the BCC. The DSMB reviewed the data and agreed that the total sample size of 500 was accurate. Therefore, the remainder of the sample will be collected in a multi-center trial. There will be approximately 200 more patients randomized to each treatment group along with the 109 patients randomized in the pilot study, would achieve the total sample size of 500 patients.

5.5 Statistical Analyses

The principal analyses of primary and secondary outcomes employ the "intent-to-treat" approach as described by Peduzzi.⁶⁰ The intent-to-treat analyses include all randomized patients with all patients included in their randomly assigned treatment group; treatment group assignment is not altered based on the patient's adherence to the assigned treatment regimen. All statistical tests are two-sided with the overall significance level of the primary outcome $\alpha=0.05$. However, the significance levels used in the interim and final analyses of the primary outcome are adjusted to account for the interim analyses.

- *Baseline characteristics:* Comparison of the baseline characteristics (e.g., age, gender, stone location and size) between the two treatment groups uses standard parametric and nonparametric statistical techniques, such as the Pearson chi-square test and Fisher's exact test for categorical data and ANOVA and the Kruskal-Wallis test for continuous data.
- *Primary outcome:* The principal analysis of STONE will be a comparison of the proportion passing stones in the two groups using the Pearson chi-square test. Logistic regression will be used if covariate adjustment is necessary.
- *Secondary outcomes:* Secondary time to event outcomes (e.g., time to passage of stone; time to pain relief) are analyzed using life-table analysis of the time to event. A proportional-hazards regression model is used to evaluate potential covariates that may modify the secondary time to event outcomes (e.g., size and location of stone). Graphical procedures are used to assess the proportionality assumption. If the proportionality assumption is found to be unreasonable, then other models such as the accelerated failure time model or the proportional odds model are used to evaluate the covariates.
- Secondary dichotomous outcomes (e.g., need for surgical intervention or lithotripsy) are analyzed using the same methods as described for the primary outcome. Ordinal outcomes (e.g., number of days lost from work) are analyzed using Poisson regression with adjustment for covariates if necessary. Continuous variables will be analyzed using general linear models.
- *Subset analysis:* It is possible that the beneficial effects of the study drug, if observed, are stronger in one subset of patients than another. Subsets based on sex, age, stone size, stone location and stone recurrence may receive differential benefit. To assess this possibility, these groups are tested as interactions with treatment group, using cross-product terms, in the appropriate model (e.g., Cox proportional hazards, logistic regression, Poisson regression).

If the two groups show a difference in the incidence of the primary outcome, interactions will be evaluated and subgroup analyses conducted to determine whether the effect prevails throughout particular subgroups of patients. Indeed, NIH guidelines require investigators to evaluate consistency between the genders and across racial subgroups. It should be noted, however, that subgroup analyses have been greatly abused,⁶¹ particularly when there is no overall treatment difference. There is a strong temptation to search for a specific subpopulation in which the therapy is nevertheless effective. Yusuf et al⁶² concluded "*the overall 'average' result of a randomized clinical trial is usually a more reliable estimate of the treatment effect in the various subgroups examined than are the observed effects in individual subgroups.*" Thus subgroup analyses will be interpreted with care.

- *Interim analysis:* The Lan-DeMets⁵⁵ spending function approach is used to adjust the probability of a type I error for testing the primary outcome when interim 'looks' of the data are taken by the

Data Safety Monitoring Board. The spending function corresponding to an O'Brien - Fleming boundary is used. The Lan-DeMets procedure is flexible, in that the number of looks does not have to be specified in advance and the time interval between looks does not have to be the same throughout the study. The rate at which the type I error is spent is a function of the fraction of total information available at the time of the interim analysis (i.e., information time).⁶³ Prior to taking any 'looks' at the data, the study Steering Committee and the DSMB will develop study-specific procedures for interim analyses and stopping rules.

6 Data Collection and Management

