The study is a multi-center randomized, placebo-controlled, double-blind clinical trial. Participants are randomized to one of two treatment groups, placebo or active tamsulosin. The primary objectives of this study are to test the hypothesis that tamsulosin is clinically useful in the treatment of acute urolithiasis. If tamsulosin achieves similar results in a properly conducted placebo controlled trial to those noted in previous smaller pilot studies, we expect to see a significant reduction in days lost from work and decreased morbidity, as well as cost savings resulting from a decreased number of patients referred for the surgical management of retained stones.

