Our data analysis is designed to evaluate the following goals of the study: 1) to determine the efficacy of tamsulosin with respect to primary and secondary outcomes in patients with urolithiasis, 2) to ensure that such treatment is safe 3) to determine if benefit is equally evident across a range of clinically relevant subgroups. The principal analyses of primary and secondary outcomes employ the intent-to-treat (ITT) approach. Although data may be missing at points in time, all relevant data available from each participant will be employed in all analyses. An ITT analysis more closely reflects actual conditions and experiences of clinical practice than analyses based on the subset of 'complete' or 'totally compliant' participation and, therefore, does not overestimate the impact of an intervention. Treatment group assignments are not altered based on adherence to the assigned treatment regimen. Furthermore, applying ITT maintains the benefits of randomization; if dropouts and non-compliers are ignored, then the study design becomes more observational and bias due to post-randomization subset selection is introduced. All significance tests will be 2-sided, with alpha=0.05.

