5.2 Interim Analysis

Interim statistical analyses of clinical trials are a requirement of all National Institutes of Health (NIH) sponsored clinical trials. The Data and Safety Monitoring Committee (DSMC) meets at least once a year to review trial results; however, the exact timing of the interim analyses is at the discretion of the committee. Before each meeting, a formal detailed statistical report will be written by the Biostatistical Coordinating Center (BCC) which presents the results of every aspect of the study, including all baseline variables, protocol adherence, all outcome variables, adverse events reported and center performance in terms of recruitment, data quality, loss to follow-up and protocol violations. However, the main emphasis is on the primary outcome. For this evaluation, a cohort of patients is chosen consisting of all patients randomized before a certain date so that the analysis cohort does not depend on time to stone expulsion.

The main statistical issue relevant to interim analysis is the problem of performing multiple tests of significance on accumulating data. A number of procedures have been developed to handle this situation^{50,51} Most techniques^{52,53} entail adjusting the nominal significance level at the interim evaluations to some value less than α , such that the overall probability of committing a type-I error is maintained at α . For this trial, the group sequential method of Lan and DeMets⁵⁴ will be used to characterize the rate at which the type I error is spent. This method is flexible with regard to the timing of

the interim analyses. Asymmetric stopping boundaries will be used for the Lan-DeMets procedure. The upper boundary which describes the stopping rule for benefit will be based on 1-sided type I error of .025 and the Lan-DeMets generalization of the O'Brien-Fleming boundary. The lower boundary will be based on a less stringent stopping rule: 1-sided type 1 error of .05 and the Lan-DeMets generalization of the Pocock type boundary. However, this should not preclude the Data and Safety Monitoring Committee recommending termination earlier if there is evidence of harm.

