5.3 Analysis Plan

5.3.1 Preliminary Analyses

To assess the efficacy of tamsulosin for the treatment of urolithiasis, the BCC will employ a systemic statistical analysis strategy. The first analytic step will be to compile descriptive statistics (e.g. mean, standard deviation, range, proportion) of patient demographics. This activity, while not directly addressing any of the study hypotheses, will serve to describe central tendencies and the variability of outcome variables and co-variables.

Then a series of interactive data analyses will be conducted, which will be used to characterize data distributions, detect any missing data patterns, examine associations and redundancies among independent variables, and generally watch for unusual or unexpected data patterns. This will help verify whether the assumptions of the proposed statistical models are reasonably met and if necessary to choose alternative analytic methods such as non-parametric tests or transformations.

The second step will be to compare treatment groups with respect to important suspected covariates, specifically age, gender, stone location and size, and the number of prior episodes of renal colic. Any variables found to have substantial imbalance (either statistically significant or large in magnitude) between the study groups will be included as covariates. The third step will be to analyze the data according to our specific aims.

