5.3.2 Testing of efficacy and safety outcomes

One of the secondary endpoints is whether the patient requires a more complicated treatment within 90 days of the index emergency visit. This would be evidenced by the need for surgical intervention or lithotripsy. Based on the practice characteristics of the research site we expect a low number of these cases. In addition, work by Yilmaz³⁶ described above lends strong evidence to our expectation that the

surgical intervention rate will be low. These cases will be described descriptively. The two study groups will be compared using the Pearson chi-square test or the Mantel-Haenszel procedure if covariate adjustment is necessary. An additional secondary outcome is the number of days of work missed. These will be tested by t-test or (or ANCOVA with covariates), or if necessary because of distributions requirements, by the Wilcoxon test.

To examine whether the treatment groups experience comparable rates of complications we will monitor patients for several unlikely but potential complications of tamsulosin as outlined above. Events not typically associated with patients with acute urolithiasis will be classified as adverse effects. Adverse and serious adverse events are expected to occur at a very low rate in both study conditions. These will be analyzed descriptively.

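### Days lost from work is given two different analyses (t-test/ANCOVA or Wilcoxon in 5.3.2, Poisson regression in 5.5), with no rule on which governs and no variance estimator for the Poisson model

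*Combined protocol and SAP*

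**What the plan says.** Section 5.3.2 introduces the outcome: "An additional secondary outcome is the number of days of work missed". It continues: "These will be tested by t-test or (or ANCOVA with covariates), or if necessary because of distributions requirements, by the Wilcoxon test". No criterion is given for moving from the t-test to Wilcoxon.

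Section 5.5, under secondary outcomes, uses the same outcome as its example for a different method: "Ordinal outcomes (e.g., number of days lost from work) are analyzed using Poisson regression with adjustment for covariates if necessary". It does not say whether standard errors are model-based, scaled or robust, and it labels a count of days as ordinal.

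The closest thing to a selection rule is in 5.3.1, where the preliminary analyses allow the team "if necessary to choose alternative analytic methods such as non-parametric tests or transformations". That sentence does not mention Poisson regression and does not rank 5.3.2 against 5.5. The opening of Section 5 and Section 5.5 both refer to principal analyses of primary and secondary outcomes, but only to set the intent-to-treat principle. The opening of Section 5 also fixes the level: "All significance tests will be 2-sided, with alpha=0.05".

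Days lost from work is one of the nine secondary outcomes listed in 4.3.2 and appears again in 3.2 and Appendix A. Section 3 names fewer lost days as an expected benefit, on a condition: "If tamsulosin achieves similar results in a properly conducted placebo controlled trial to those noted in previous smaller pilot studies".

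**The concern.** Two analysts following the same plan could report different things. Section 5.5 leads to a ratio of mean days. Section 5.3.2 leads to a difference in mean days or, after an undefined switch, to a rank comparison. The estimate therefore depends on the section chosen even when the significance verdict does not.

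The verdict can also move, in two ways. First, Poisson regression with model-based errors assumes that the variance equals the mean. If days lost vary more than that, the standard errors are too small, the confidence interval is too narrow and the test rejects too often. Second, within 5.3.2 the t-test and Wilcoxon address different features of the distribution, and the choice between them is left to be made after the data are seen.

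**Working it through.** **Inputs from the documents.** Two-sided alpha 0.05 (opening of Section 5); 250 per group and a placebo passage rate of 0.45 (5.4.1). There is no planning figure for days lost to reproduce. The 250 belongs to the primary outcome and only supplies n here. As a check on it, 0.45 versus 0.60 at 90% power with the pooled chi-square needs 231 per group; 250 gives 92.1% power, or room for 1 − 231/250 = 7.6% loss.

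**Assumed.** The variance/mean ratio φ and the mean number of days, neither of which the documents give.

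**Formula.** If the true variance is φ times the mean, a model-based Poisson z-statistic has variance φ instead of 1 under the null. So:

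- type I error = 2Φ(−1.96/√φ)
- coverage of the 95% interval = 1 − type I error
- width of a correct interval relative to the model-based one = √φ

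**Check by simulation.** 10,000 null trials per cell, 250 per arm, means of 2, 3 and 5 days, Poisson counts at φ = 1 and negative binomial counts above it. Ranges are over the three means. Simulation error near 5% is about 0.2 percentage points.

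| φ | Model-based Poisson, formula | Model-based, simulated | Robust Poisson | t-test | Wilcoxon |
|---|---|---|---|---|---|
| 1 | 5.0% | 5.2–5.3% | 5.2–5.4% | 5.1–5.3% | 5.2–5.3% |
| 1.5 | 11.0% | 10.7–11.3% | 5.0–5.4% | 4.8–5.2% | 4.8–5.2% |
| 2 | 16.6% | 16.7–17.1% | 4.9–5.3% | 4.8–5.1% | 4.9–5.4% |
| 3 | 25.8% | 25.5–26.3% | 4.8–5.6% | 4.6–5.3% | 4.8–5.3% |
| 5 | 38.1% | 36.6–38.8% | 5.2–5.4% | 5.0% | 4.9–5.2% |

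Share of the same null trials in which two methods fall on opposite sides of 0.05:

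| φ | Model-based Poisson vs t-test | Robust Poisson vs t-test | t-test vs Wilcoxon |
|---|---|---|---|
| 1 | 0.5–0.6% | 0.1% | 2.2–2.3% |
| 1.5 | 5.9–6.1% | 0.2% | 2.7–3.1% |
| 2 | 11.9–12.1% | 0.1–0.2% | 3.1–3.5% |
| 3 | 20.9–21.1% | 0.2–0.4% | 3.2–4.5% |
| 5 | 31.6–33.7% | 0.2–0.4% | 3.9–5.3% |

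**Is φ above 1 plausible?** A mixture of patients who pass the stone and patients who do not would produce it. Take 45% passers, and assume a mean of 1 day for passers, m for non-passers, and Poisson variation within each group. Then φ = 1 + 0.45 × 0.55 × (m − 1)² / (0.45 + 0.55m).

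- m = 2: 1 + 0.2475/1.55 = 1.16, type I error 7%
- m = 3: 1 + 0.99/2.10 = 1.47, 11%
- m = 4: 1 + 2.2275/2.65 = 1.84, 15%
- m = 5: 1 + 3.96/3.20 = 2.24, 19%

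The day counts are invented for the illustration; only the 45% comes from the plan.

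**The case against.** **The large figures belong to a conditional problem.** The plan does not say that model-based errors will be used; it is silent. Section 5.3.1 tells the analyst to check model assumptions and change method if needed, and a competent check could catch overdispersion. This stands. A reader might infer that the trial will test this outcome at 19% or 38%, but the documents support neither model-based errors nor any value of φ. Nor is any of these figures a ceiling, since a larger φ gives a larger error.

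**Section 5.5 looks like the governing text.** It gives the current primary test and sorts secondary outcomes by type, while 5.3.2 is partial, and the subset paragraph of 5.5 again lists Poisson regression. That makes 5.5 the more natural reading, but it remains inference: 5.3.2 names the outcome and its tests explicitly and nothing withdraws it.

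**The choice of section hardly moves the verdict if the Poisson errors are robust.** This also stands: robust Poisson and the t-test rarely disagree. What remains is the different effect measure and the Wilcoxon switch.

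**Robust Poisson is not the only sound answer.** Correct. The t-test already in 5.3.2 holds its level as well. It would also be wrong to read the plan as inviting the analyst to pick the smallest p-value; it proposes no such thing.

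**Conclusion.** The contradiction is certain and rests on the text alone: one outcome, two analyses with different effect measures, no ranking. The general licence in 5.3.1 does not settle it.

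Inflation of the type I error is conditional on two things that the documents leave open: model-based Poisson errors and a variance above the mean. The two robust conclusions are comparative. Across every ratio tried, robust Poisson and the t-test stay near 5% and disagree in no more than about 0.3–0.4% of null trials. The t-test and Wilcoxon disagree in about 2–5%, so the switch without a criterion deserves the same attention as the Poisson variance.

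Severity is low. This is one secondary outcome; the primary chi-square comparison and the sample size do not depend on it.

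**What to change.** Make 5.3.2 and 5.5 name the same single governing analysis for days lost from work, with its variance estimator. Either of these would do:

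- Poisson regression with robust (sandwich) standard errors, reporting the ratio of mean days with a 95% CI. This keeps the model in 5.5.
- The t-test, or ANCOVA with covariates, reporting the difference in mean days with a 95% CI. This keeps the method in 5.3.2.

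Label the remaining methods, including Wilcoxon, as sensitivity analyses, so that no data-driven switch is needed. Call the outcome a count. If a treatment interaction is tested with Poisson regression on this outcome, use the same robust errors.

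Do this before any further comparative analysis. Section 5.2 describes an interim report "which presents the results of every aspect of the study, including all baseline variables, protocol adherence, all outcome variables", and 5.4.1 says that the monitoring board has already reviewed data from the first 100 patients; the documents do not say whether days lost were compared then.

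The cost is wording in two sections and, for the Poisson option, one line of code. Its robust interval is wider than the model-based one by √φ: unchanged at a ratio of 1, about 22% wider at 1.5, 41% at 2 and 73% at 3. Where φ exceeds 1, that extra width is what valid coverage requires.

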6.1 Data Collection Forms

Data will be collected on standardized forms on which nearly all responses have been pre-coded. Each form is briefly described below:

- Screening Log lists all patients screened for the study and some demographic data.
- Eligibility and Randomization Form is completed for all randomized patients and records assigned study drug code number, and information on the study drug administration.
- Screening Form is completed for all randomized patients. This form includes detailed medical data obtained during screening for the study.
- Adverse Event Form records adverse events.
- Follow-up Form for all contact calls for follow-up of randomized patients.
- Radiologic Imaging Forms for radiologic imagining at screening and at follow-up.

6.2 Web Data Entry System

For this protocol, web data entry screens corresponding to the study forms listed above will be developed and maintained by the staff of the BCC. Clinical center staff will enter data into the MySQL database located at the BCC through a web data management system (MIDAS). The data are edited on-line for missing, out of range and inconsistent values. A Users' Manual documenting this system is provided to the centers by the BCC.

